Expected Result: An FES paradigm involving ergometry of the upper extremities will enhance subjects' functional recovery, as measured in the clinic by neurological and anatomical indices.

VIII. INCLUSION / EXCLUSION CRITERIA

a. Inclusion criteria:

- a. Male, Female, age 18-55, all ethnic groups.
- b. Spinal Cord Injury, traumatic and non-traumatic.
- c. C1-C6 neurological level.
- d. ASIA class A or B.
- e. Chronic injury,>12 months and < 20 years from the injury.
- f. No upper-extremity electrical stimulation in the previous 4 weeks.
- g. Subjects are medically stable, with no recent (1 month or less) inpatient admission for acute medical or surgical issues.
- h. Baseline physical activity will be kept stable during the study.
- i. Pain and antispasticity medications dose will be kept stable during the study.
- j. Subjects are legally able to make their own health care decisions.

b. Exclusion criteria:

- a. Associated lower motor neuron/peripheral nerve injury in the C1-C6 levels.
- b. Presence of pacemaker.
- c. Presence of cancer.
- d. History of seizures.
- e. Women who are pregnant.

IX. SUBJECT RECRUITMENT & SCREENING**a. Subject recruitment & screening:**Recruitment scenario 1:

Patients of the ICSCI, and prior study participants will be identified as meeting the inclusion criteria by reviewing the medical records held by the ICSCI and filling out a Medical Chart Review Form. A waiver of privacy authorization will be obtained from the local IRB of Record [HIPAA Form4] prior to chart review. Patients will be told about the study during a clinical visit; they will be given a Subject Recruitment Flyer with contact information; a note of this communication will be made in the patient's medical record. Those who are interested can meet privately with, or contact later the principal investigator or study coordinator who will explain in simple terms: 1) the purpose of the research and the procedures involved, 2) potential benefits, 3) potential risks, 4) the subject's right to withdraw at any time without penalty of any sort, and 5) assurance of anonymity. If a patient indicates that he/she is no longer interested or is not eligible, the Medical Chart Review Form will be shredded.

Recruitment scenario 2:

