Subject Recruitment Flyers will be posted at KKI and outside medical facilities who have agreed to do so. Physicians at KKI and these outside facilities will be provided with a guide to inform them generally of the exclusion/inclusion criteria for the study, and extra copies of the flyer to give out to potential subjects. The Subject Recruitment Flyer will be posted on the ICSCI website (www.spinalcordrecovery.org) and 3rd party websites who have agreed to do so. The Study will also be listed on the newsletter published periodically by ICSCI and KKI. The Study will also be listed on KKI Facebook social networking page (<http://www.facebook.com/kennedykrieger>) and other social network sites as appropriate. This study will also be registered on www.clinicaltrials.gov within one year from initial IRB approval. This study can also be posted on and www.centerwatch.com. This study will also be advertised on the KKI on-hold message phone system. This study will be also discussed in a Press Release. All potential subjects who contact us in respond to the recruitment flyers will be called back by the study coordinator to complete a phone screening interview to determine initial eligibility documented in a Phone Screening Form. A waiver of privacy authorization will be obtained from the local IRB of Record [HIPAA Form4] prior to phone screening interview. The study coordinator will explain in simple terms: 1) the purpose of the research and the procedures involved, 2) potential benefits, 3) potential risks, 4) the subject's right to withdraw at any time without penalty of any sort, and 5) assurance of anonymity. If the potential subject is interested in participating, study coordinator will ask the potential subject questions about his/her medical history. The principal investigator or co-investigators will review the potential subject's medical history to ascertain if inclusion criteria are met and that there are no obvious exclusions. The potential subject will be called back to indicate if they are eligible to participate. If a potential subject indicates that he/she is no longer interested or is not eligible, the Phone Screening Form will be shredded.

For all recruitment scenarios:

If the potential subject meets the inclusion criteria and agrees to participate, the subject will receive a copy of the Informed Consent Form. The potential subject will be allowed as much time as needed (up to 1 month) to

Version/Date: 11.0, 16-Sept-2013

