The randomized sequence will be generated by using the Web site Randomization.com (<http://www.randomization.com>) using the Random Block Size method for 24 subjects in two groups. The sequence will be stored electronically in a password-protected document.

The Research Coordinator 1 is assigned to:

- Manage the randomized sequence electronic file.
- Assign participants to subgroups according to the randomized sequences.

c. HIPAA Compliance

As per the Local IRB of Record Consent Form Template, the HIPAA compliance/authorization language is included in the Consent Form.

d. Pregnancy:

As per the local IRB of Record, pregnant participants are typically excluded from protocols using ionizing radiation. Also, while there are no known risks to an embryo or fetus associated with FES during pregnancy, this research may hurt an embryo or fetus in ways we do not currently know. For this reason, pregnant women cannot take part in this study. If a woman is capable of having children, she must have a pregnancy test. The pregnancy test will be performed during the post-consent screening. If the subject becomes pregnant (or suspect pregnancy) before this study is completed, the subject must inform the study team immediately.

XI. DATA COLLECTION and ANALYSIS

a. Study Procedures

1. Study design, including the sequence and timing of study procedures (distinguish research procedures from those that are part of routine care).

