The study subjects will engage in an A (upper extremities FES assisted ergometry)-B (upper extremities non-FES assisted exercises) type protocol intervention in which they undergo either 4 months of FES assisted upper extremity ergometry followed by 1 month wash out period, then by 4 months of a specific, individualized, non-FES assisted exercise regimen (strengthening, stretching, splinting) or 4 months of an upper extremities non-FES assisted exercise protocol followed by 1 month wash out period, then by 4 months of FES assisted upper extremity ergometry. 12 subjects randomly selected will start with the FES assisted intervention and the other 12 subjects will start with the non FES assisted regimen. FES will be delivered using the RT300-SLSA Cycle Ergometer, Restorative Therapies, Inc. The subjects will be assessed using a battery of physical and neurological indicators before starting the intervention (time 0), after completing first 4 months of intervention (4 months), after the 1 month wash out (5 months), after completing the second 4 month of intervention (9 months) and 3 months after completing the last intervention (12 months). The evaluator will be blinded to group assignment, but we cannot use true blinding due to the intervention's sensory component. The Study Time Line is found in Figure 1.

[figure not shown]

Figure 1: Study Time Line

(1) Assessment:

The tests listed below will be performed for all subjects. The data collection schedule in Table 1.

a) Neurological Exam: This is a routine exam performed to rule out any associated lower motor neuron/peripheral nerve injury in the C1-C6 levels. Subjects will undergo testing of the deep tendon reflexes at the biceps, brachio-radialis and triceps level. This involves tapping of each specified muscle tendon with a neurologic reflex hammer.

b) Fast Urine Pregnancy Test: This is a routine exam performed for women of child bearing age who do not take any birth control prophylaxis.

c) Severity of gleno-humeral subluxation: This is a routine exam performed to assess shoulder subluxation. The space between the glenoid and head of the humerus can be visualized on plain X-rays and measured, in centimeters, to grade severity. This test is done bilaterally.

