q) Non-FES Upper Extremity Exercise: While undergoing the non-FES exercise intervention, the subjects will receive a specific, individualized exercise regimen, consisting of strengthening, stretching, splinting and any other therapeutic interventions that do not use electrical stimulation.. The subjects will remain seated in their primary wheelchair throughout the treatment. The subjects will exercise for 60 minutes/session, three times a week for 4 months.

2. Study duration and number of study visits required of research participants.

The study will last 12 months. The Study Time Line is found in Figure 1, and the Data Collection Schedule in Table 1.

(1) Assessment:

The following post-consent screening will be performed at the Initial visit:

- a. Neurological Exam (about 30 minutes)
- b. Fast Urine Pregnancy Test (about 15 minutes)

The following assessments will be performed at the Initial Visit:

- o. FES Evaluation (about 15 minutes)

The following assessments will be performed at the Initial, 4th month, 9th month, and 12th month Visits:

- c. Severity of gleno-humeral subluxation (about 30 minutes)

The following assessments will be performed at the Initial, 4th month, 5th month, 9th month, and 12th month Visits:

- d. Spasticity measurement (about 15 minutes)
- e. Capabilities of the Upper Extremity test (about 10 minutes)
- f. Jebsen-Taylor Hand Function test (about 15 minutes)
- g. Box and Blocks test (about 15 minutes)
- h. Action Research Arm test (about 20 minutes)
- i. Functional Reach test (about 5 minutes)
- j. Range Of Motion of the upper extremity joints (about 30 minutes)
- k. Numerical Rating Scale (NRS) for pain (about 1 minutes)
- l. Pulmonary Function Test (PFTs) (about 5 minutes)
- m. American Spinal Injury Association (ASIA) exam (about 60 minutes)
- n. Pain and Spasticity Medication inventory (about 10 minutes)

	Initial	4 th Month	5 th Month	9 th Month	12 th Month	Test Evaluator*	Blinded
	5 hours	4 1/2 hours	3 2/3 hours	4 1/4 hours	4 1/4 hours		
Neurological Exam	√					PI, CoI1	No
Fast Urine Pregnancy	√					N1, N2, N3	No
Shoulder X-Ray	√	√		√	√	PI, CoI3	Yes
Modified Ashworth	√	√	√	√	√	PI, CoI1	Yes
CUE	√	√	√	√	√	T1,T6	Yes
JTHF	√	√	√	√	√	T1,T6	Yes
BB	√	√	√	√	√	T1,T6	Yes
ARA	√	√	√	√	√	T1,T6	Yes
FR	√	√	√	√	√	T1,T6	Yes
ROM	√	√	√	√	√	T1,T6	Yes
Pain NRS	√	√	√	√	√	PI, CoI1, SC2	No
PFTs	√	√	√	√	√	N1, N2, N3	No
ASIA	√	√	√	√	√	PI, CoI1	Yes
Meds Inventory	√	√	√	√	√	PI, CoI1, N1, N2, N3, SC2	No
FES Eval	√					T1,T6	No

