Accurate and complete study records will be maintained and made available to representatives of the U.S. Army Medical Research and Materiel Command. These representatives are authorized to review research records as part of their responsibility to protect human research volunteers. Research records will be stored in a confidential manner so as to protect the confidentiality of subject information.

XIII. RISK AND INJURY

a. Risks, Risk Management:

All assessments and intervention sessions will be supervised by the Principal Investigator.

For all the study procedures, the risks and risk management are defined in the sections below.

1. Assessment Risks:

a) Neurological Exam: During testing, the subject might experience pain induced by hitting/tapping of the arm, but usually, the sensation experienced is a quick, non-painful touching sensation. To minimize the risk, one of the study team member trained in the procedure will perform the test.

b) Fast Urine Pregnancy Test: There is the possibility of psychological stress occurring if testing shows that the subject may be pregnant. To minimize the risk in the event that pregnancy test results are positive, the result will be disclosed to the subject. If the subject is uncomfortable with this arrangement, his/her consent to participate in this study is not recommended.

c) Severity of gleno-humeral subluxation: The subjects receive ionizing radiation due to the diagnostic bilateral shoulder X-ray procedures they receive at the Initial, 4th Month, 9th Month, and 12th Month visit. The Total Effective Dose from the procedures is 0.4 rem. This is more than the 0.3 rem that the average person in the United States gets each year from natural sources like the sun, outer space, air, food and soil. It is less than the 5 rems of radiation that is allowed each year for people who are exposed to radiation in their jobs. To minimize the risk, pregnant women are excluded from the study.

d) Spasticity Measurement: There is a risk of eliciting spasms during the test. Subjects will feel a quick pull of the muscle, which might be painful at times. To minimize the risk, one of the study team member trained in the procedure will perform the test.

e) Capabilities of the Upper Extremity (CUE) test: There are no known risks associated with this test.

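### The protocol gives two rules for who has the entry pregnancy test, and under the narrower one a woman on contraception can enter untested

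*Combined protocol and SAP*

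**What the plan says.** Section X.d (Pregnancy) sets a mandatory rule with no exception for contraception: "If a woman is capable of having children, she must have a pregnancy test". It also fixes the time: "The pregnancy test will be performed during the post-consent screening".

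Section XI.a.1 (1) (Assessment), item b), describes the Fast Urine Pregnancy Test differently: "This is a routine exam performed for women of child bearing age who do not take any birth control prophylaxis".

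Section XI.a.2 (1) lists the test under post-consent screening at the Initial visit, at about 15 minutes. Table 1 ticks it at that visit only. Neither says which women receive it.

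The test serves exclusion criterion e in section VIII.b, "Women who are pregnant". Section XIII.a.1, item c), relies on that exclusion for the radiation risk of the shoulder X-rays: "To minimize the risk, pregnant women are excluded from the study".

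**The concern.** Both sections concern the same single test but name different groups. Women who can conceive and use birth control are tested under X.d and are outside the group named in item b). Contraception does not rule out pregnancy at entry, and an early pregnancy may be unknown to the woman herself. That is the case an entry test is meant to catch.

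Where item b) is followed, the pregnancy exclusion goes unverified by any test in these women. The mitigation named for the X-rays then rests on weaker checks: chart review, a review of "medical history to ascertain if inclusion criteria are met and that there are no obvious exclusions" (section IX.a, recruitment scenario 2), and the subject's own duty under X.d to report a known or suspected pregnancy. Following item b) would also put the site in breach of X.d.

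The point is confined to who receives this one baseline test. Its timing is consistent across sections, and pregnancy arising after baseline is a separate matter.

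**Working it through.** The check is mainly a comparison of text. The plan gives no figure of its own on this point to reproduce.

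**Same test?** Yes. X.d places its test in post-consent screening, and XI.a.2 (1) lists the Fast Urine Pregnancy Test under post-consent screening at the Initial visit. The protocol schedules no other pregnancy test.

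**Who is tested under each rule?**

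| Group | X.d | XI.a.1 (1) b) |
|---|---|---|
| Able to have children, no birth control | Tested | Tested |
| Able to have children, on birth control | Tested | Not in the group named |
| Not able to have children | Not required | Not in the group named, unless of reproductive age and not on birth control |

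The second row is the one that matters for safety.

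**Does any other text settle it?**

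- The lead-in to the list in XI.a.1 (1) says the tests apply to all subjects. That cannot hold literally for a pregnancy test, and item b) narrows it.
- XI.a.2 (1) and Table 1 give the visit and not the population.
- XIII.a.1, item b), covers the stress of a positive result and its disclosure, and does not say who is tested.
- The phrase in X.d about being able to have children is nowhere defined to leave out women on contraception.
- No section states which rule prevails.

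**What exposure should the test precede?** Section XIII.a.1, item c), states: "The Total Effective Dose from the procedures is 0.4 rem". The X-rays are at the Initial, 4th, 9th and 12th month visits, so there are four X-ray visits. Assuming equal dose at each:

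0.4 rem / 4 visits = 0.1 rem at the Initial visit.

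The FES evaluation takes place at the same visit. These are the exposures that come directly after the entry test. If the pregnancy stayed unrecognised, study sessions and possibly later X-rays would follow, to an extent that depends on when it was noticed. The 0.1 rem is the subject's effective dose; the documents give no fetal dose. For FES, X.d reports no known risk to an embryo or fetus but allows for unknown harm.

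**How many women?** This cannot be calculated. Section IX.b plans up to 30 enrolled and 24 accrued, with no sex split and no contraception rate. Those totals only bound the number.

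**What would the wider rule cost?** At about 15 minutes per test, an absolute ceiling is:

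30 × 15 min / 60 = 7.5 hours.

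This treats all 30 enrolled as needing an added test, including men and women who would be tested anyway, so the real figure is well below it.

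**The case against.** The strongest reply is that the sentences can be read together. Item b) does not say that nobody else is tested, so a site that follows X.d tests everyone item b) names and satisfies both. Section XI.a.1 asks the protocol to separate research procedures from routine care, and nearly every item in the list opens with the same routine-exam formula. On that reading item b) describes where the test is usual practice, and X.d, with its mandatory wording and stated time, is the operative rule.

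This reading is possible, but the text does not compel it. Item b) is the only statement in the procedures section of who has the test, and a coordinator working from that section could reasonably treat it as the rule. At best an ambiguity remains in a safety check, and it needs the same correction.

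It is also fair to say that harm needs several things together: staff follow the narrower sentence, a woman on contraception is pregnant at entry, and she does not suspect it. Nobody can show from the documents that even one subject would be affected. That limits the size of the concern, and the conclusion is worded accordingly. It is likewise right that this is an inconsistency of wording with no bearing on outcomes, randomization or analysis.

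**Conclusion.** The concern holds. The protocol states two populations for one entry test and does not reconcile them. Under the narrower statement, a pregnancy present at entry in a woman on contraception can go untested, which leaves the pregnancy exclusion and the stated X-ray mitigation unverified for her.

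The number affected is unknown and probably small, within at most 30 enrolled. The X-ray exposure at the Initial visit is about 0.1 rem on the equal-dose assumption, with no fetal dose available. The consequence is conditional on staff acting on item b). The correction should be made because it concerns a safety-relevant eligibility check and adopts a rule the protocol already contains. It changes nothing in the statistical plan.

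**What to change.** Replace the sentence in section XI.a.1 (1), item b), with the X.d rule, for example: *Performed at post-consent screening, before the first X-ray and the FES evaluation, for every woman capable of having children, regardless of contraception.*

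Then check that the screening form listed in section XXI.c carries the same rule. Its content is not available here, so no mismatch is claimed.

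The cost is one sentence, one form check and a few extra urine tests, well under the 7.5-hour ceiling.

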* PI: Principal Investigator, CoI1: Co-Investigator 1, CoI3: Co-Investigator 3, T1-7: Therapist 1-7, N1: Nurse 1, N2: Nurse 2, N3: Nurse 3, SC2: Study Coordinator2.

Table 1: Data Collection Schedule

(2) Intervention:

There are a total of 96 visits: 48 FES assisted intervention visits scheduled 1 hour, 3 times a week for 4 months, and 48 non-FES assisted exercise regimen visits scheduled 1 hour, 3 times a week for 4 months.

3. Blinding, including justification for blinding or not blinding the trial, if applicable.

The evaluator will be blinded to group assignment for the following assessment, but we cannot use true blinding due to the intervention's sensory component:

- c. Severity of gleno-humeral subluxation
- d. Spasticity measurement
- e. Capabilities of the Upper Extremity test
- f. Jebsen-Taylor Hand Function test
- g. Box and Blocks test
- h. Action Research Arm test
- i. Functional Reach test
- j. Range Of Motion of the upper extremity joints
- m. American Spinal Injury Association (ASIA) exam

4. Justification of why participants will not receive routine care or will have current therapy stopped.

All subjects will continue to consistently perform their usual (“baseline”) amount of physical activity throughout the study, including performance of lower extremities assisted FES ergometry, home exercise stretching program, cardiovascular conditioning, etc. “Baseline” activity is defined as amount of physical activity performed for at least 1 month prior to enrollment. Routine care will not be interrupted.

5. Justification for inclusion of a placebo or non-treatment group.

Both groups will receive some type of intervention: upper extremity passive ergometry or FES assisted upper extremity ergometry. This way, the effect of FES application will be extracted.

6. Definition of treatment failure or participant removal criteria.

Treatment failure constitutes of:

- Increased pain (more than 3 points increase on the NRS).
- Increased shoulder subluxation (more than 1 cm).
- Decreased range of motion (more than 15 deg).

Subjects will be removed from the study if they:

- Requires significant hospitalization (that would interfere with physiologic processes proposed to be studied through the protocol, i.e. e-stim) – at the discretion of PI.
- Become pregnant.

7. Description of what happens to participants receiving therapy when study ends or if a participant's participation in the study ends prematurely.

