- 1] allows the stimulation of our proposed list of upper extremity muscles (supraspinatus; infraspinatus; teres major and minor; anterior, middle, or posterior deltoid; biceps; and triceps), which is more than the standard set of muscles (bilateral biceps, triceps and supraspinatus).
- 2] allows to change the timing of the stimulation (On/Off) to produce a smooth cycling motion.

4. FDA approved use description:

The device FDA indication for use are:

1. Relaxation of muscle spasms
2. Prevention or retardation of disuse atrophy
3. Increasing local blood circulation
4. Maintaining or increasing range of motion

5. IDE Info:

Not applicable

c. Study Statistics

1. Primary outcome variable.

Independent Variables

FES or no FES

Dependent Variables: to be measured at 0, 4, 5, 9 and 12months

Severity of gleno-humeral subluxation, measured by X-ray (not measured at 5 months).

Spasticity of the pectoralis, biceps, triceps, and long finger flexor muscles, measured with the Modified Ashworth.

Functional movement of the shoulder, measured with the Capabilities of the Upper Extremity (CUE) test.

Hand function, measured with the Jebsen-Taylor Hand Function (JTHF) and Box and Blocks (BB) tests.

Upper limb function measured with the Action Research Arm test (ARA) test.

Range Of Motion of the upper extremity joints (of the shoulder, elbow, wrist, and fingers/thumbs), measured with goniometry.

Pain, measured with the Numerical Rating Scale (NRS).

Neurological function, measured with the American Spinal Injury Association (ASIA) exam.

2. Secondary outcome variables.

Not applicable

3. Statistical plan including sample size justification and interim data analysis.

Data Analysis: Data will be collected in accordance with each instrument's standardized instructions, with the evaluator being blinded to group assignment. To obtain consistency and facilitate interpretation of the data, we will use means and standard deviations (SDs) to describe normally as well as non-normally distributed variables. Appropriate post-hoc statistical analysis will be used to compare between group means and repeated measures. Baseline tests of homogeneity will be used *a priori*. If statistically significant differences are found after the subjects are randomized to the two groups, they will be corrected in the post-hoc analysis. Results will be considered significant at $P<0.05$.

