o) FES: The risk associated with FES is pain at the stimulation site. To minimize the risk, stimulation will only be done to the participant's tolerance level. There is a minimal risk of skin burn. To further **minimize the risk** of skin burn, only appropriate size electrodes will be used and they will be replaced as per the manufacturer's recommendations.

3. *Other Risks:*

p) Time Commitment: The time commitment to the 3 visits per week for 4 months may be inconvenient. To minimize the risk: 1] The subject should contact the study coordinator if having problems scheduling the visits; 2] If we feel that the subject can not commit the time and effort, he/she will be excluded from the study; 3] The visits may cause moderate social, school and work disruption. The start of the study will be scheduled to lessen the disruption.

b. Medical Care For Research Related Injury:

For greater than minimal risk studies, the USAMRMC can commit to providing treatment to research volunteers free of charge in an Army medical facility, therefore the ORP HRPO mandated language shall be included in the consent form.

XIV. BENEFIT(S)

There are no known benefits for those who participate in this study. The possible benefits to the participant from upper extremity FES ergometry include muscle mass and strength increase, muscle tone decrease, cardiovascular conditioning. This study may benefit others in the future by helping understand how upper extremity ergometry with FES might contribute to an improved quality of life for people with cervical spinal cord injuries.

XV. COMPENSATION

a. Payment and Remuneration:

Subjects will be paid a total of \$250.00 if they complete the study. Of this amount, \$20.00 is a bonus, which the subjects will be eligible to receive if they have shown up on time for all study visits as scheduled, and followed the directions of the study staff.

If the subjects do not finish the study, they will be paid only for the amount completed as follows:

\$30.00 for the Initial Visit

\$25.00 for the 1st month of FES treatment

\$25.00 for the 2nd month of FES treatment

\$25.00 for the 3rd month of FES treatment

\$25.00 for the 4th month visit

\$25.00 for the 5th month visit

\$25.00 for the 9th month visit

\$50.00 for the 12th month visit

Payment will be made by check at the final visit.

b. Costs

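### Table 1 lets both Modified Ashworth and ASIA raters also collect unblinded pain and medication data, and the PI supervises treatment sessions, so blinding of these two primary instruments is not secured after baseline

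*Combined protocol and SAP*

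**What the plan says.** Table 1 (XI.a.2) gives, for each test, the visits, the permitted evaluators and a Blinded column. The two rows at issue read "Modified Ashworth √ √ √ √ √ PI, CoI1 Yes" and "ASIA √ √ √ √ √ PI, CoI1 Yes". The Pain NRS row lists the PI, CoI1 and Study Coordinator 2 (SC2). The medication inventory row lists "PI, CoI1, N1, N2, N3, SC2", where N1 to N3 are nurses. Both of these rows are marked No for blinding and are ticked at the same five visits.

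Section XI.a.3 says "The evaluator will be blinded to group assignment for the following assessment" and then names nine assessments. Ashworth (item d) and ASIA (item m) are on that list; pain (k) and medication (n) are not. Section XI.c.3 describes data collection "with the evaluator being blinded to group assignment", with no exception by instrument.

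Section XI.c.1 lists both instruments among the primary outcomes: "Spasticity of the pectoralis, biceps, triceps, and long finger flexor muscles, measured with the Modified Ashworth" and "Neurological function, measured with the American Spinal Injury Association (ASIA) exam". Section XIII.a has the PI supervising every assessment and every treatment session. Section X.b gives the randomization file to Research Coordinator 1.

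**The concern.** Subjects know which intervention they are receiving, and the protocol accepts this. Protection against biased rating therefore rests on the evaluator. Ashworth and ASIA both depend on an examiner's judgment, so they need that protection.

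Table 1 allows the person who grades spasticity and neurological function to be the same person who asks the subject about pain and medication in a role that need not be blinded. Those conversations can give the treatment away. Section XIII.a.2 states that "The risk associated with FES is pain at the stimulation site". The medication inventory records antispasticity drugs, and the Background reports that more than half of the earlier FES subjects stopped Baclofen. Doses are meant to stay stable here (VIII.a), so a reported reduction would stand out to the person about to grade spasticity.

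If the rater learns the treatment, a difference between FES and non-FES periods on these two instruments could partly reflect expectation, and the analysis could not separate that from a treatment effect.

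**Working it through.** The plan gives no figure to reproduce. The check sets the rows of Table 1 side by side and reads them against the text.

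| Test | Listed evaluators | Blinded | Visits |
|---|---|---|---|
| Modified Ashworth | PI, CoI1 | Yes | 0, 4, 5, 9, 12 months |
| ASIA | PI, CoI1 | Yes | 0, 4, 5, 9, 12 months |
| Pain NRS | PI, CoI1, SC2 | No | 0, 4, 5, 9, 12 months |
| Medication inventory | PI, CoI1, N1, N2, N3, SC2 | No | 0, 4, 5, 9, 12 months |

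1. **Overlap of people.** Listed Ashworth and ASIA raters: 2. Of these, 2 also appear in both rows marked No.
2. **Alternatives already listed.** Pain NRS: 3 − 2 = 1 of 3 evaluators (SC2) is not an Ashworth or ASIA rater. Medication: 6 − 2 = 4 of 6 (N1, N2, N3, SC2). The table permits the overlap but does not force it.
3. **Visits exposed.** The initial assessment comes before any study intervention (XI.a.1), so there is no treatment experience to reveal. That leaves 5 − 1 = 4 visits: months 4, 5, 9 and 12.
4. **Share of the primary set.** XI.c.1 lists X-ray subluxation, Ashworth, CUE, JTHF, BB, ARA, range of motion, pain NRS and ASIA, which makes 9. The point concerns 2 of them.
5. **Persistence.** There are only two sequences: FES then non-FES, or the reverse. A rater who learns a subject's first treatment at month 4 also knows the second, and so knows the treatment history at months 5, 9 and 12. Swapping PI and CoI1 between visits would not restore blinding for whichever of them had learned it.
6. **Separation rule.** No section says which listed evaluator tests a given subject, in what order the tests are done, or whether the rater may see the pain and medication forms first.
7. **PI.** XIII.a has the PI supervising every treatment session. FES cycling and non-FES exercise are visibly different, so supervision in any ordinary sense shows which one a subject is receiving. Table 1 nevertheless marks the PI as a blinded rater.
8. **CoI1.** No section gives CoI1 a role in treatment sessions or access to the allocation. The only route the documents leave open is the pair of rows marked No. If the PI is set aside because of step 7, CoI1 is the only listed Ashworth and ASIA rater who could still be blinded, so closing that route matters in its own right.

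**The case against.** A reader might infer from Table 1 that blinding fails outright for every listed rater, because nobody can be both blinded and unblinded for one subject at one visit. The documents do not support that, for three reasons.

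- The evaluator entries read as pools. SC2 or a nurse could take the pain and medication items, or one physician could take them while the other rates. This stands.
- No need not mean that the person knows the allocation. The same column marks the neurological exam and the pregnancy test No. Both are screening tests, and X.b assigns a study number only after the subject has qualified. There, No most naturally means that blinding is not required. This stands as a possible reading for pain and medication too. XI.a.3 describes blinding as a property of the evaluator for a listed set of tests, and the looser reading still leaves no safeguard for the people who do both.
- Nothing shows that CoI1 knows any allocation. This stands.

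The disclosure route can also be called thin. The NRS is one number and takes about 1 minute, and the medication inventory records doses over about 10 minutes. The ASIA exam keeps the rater with the same subject for about 60 minutes, which offers more opportunity for a stray remark. At months 5 and 12 any study stimulation ended at least 1 and 3 months earlier, so site pain is a weak cue at those visits. Much of this is fair: neither item asks about treatment, and separating the roles does not stop a subject from talking during the exam. But a cue picked up at month 4 carries forward, and a known risk of disclosure during the exam is no reason to leave a second one open.

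For the PI, it could be argued that supervision means overall responsibility and not presence in the room. XIII.a does not say so.

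**Conclusion.** The point holds as a gap in the plan. Evaluator blinding of Modified Ashworth and ASIA, as stated in XI.a.3 and XI.c.3, is not secured at months 4, 5, 9 and 12. The PI's blinding is undermined by the supervision statement in XIII.a, assuming that supervising a session means knowing which intervention is being given. For CoI1 a breach is possible but not demonstrated.

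The reach is 2 of 2 listed raters, 2 of 9 primary instruments and 4 of 5 visits. The documents contain nothing from which to estimate how far ratings would move, so no bias figure is given and the conclusion does not depend on one. The case for acting is that both instruments are examiner-judged and primary, and that the repair is cheap.

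**What to change.** - In Table 1, remove PI and CoI1 from the Pain NRS and medication inventory rows. This leaves SC2 for pain and N1 to N3 or SC2 for medication, all of whom are already listed.
- Add a sentence to XI.a.3: whoever rates Ashworth or ASIA for a subject conducts no pain, medication or treatment interview with that subject at any post-baseline visit, and does not see those forms before rating.
- Reconcile XIII.a with Table 1 so that a person who supervises a subject's intervention sessions does not rate that subject's Ashworth or ASIA; for example, CoI1 rates. Without this step the table edits do nothing for the PI.

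The cost is two table cells, one added sentence and the XIII.a reconciliation, with no extra staff or visits. Visit scheduling becomes slightly less flexible. If CoI1 becomes the sole rater, the plan should also say who covers an absence under the same rule.
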